6.2.2.2. Study Phases for Concomitant Medication

Study Phase	Definition
Pre-Treatment	Concomitant medication (CM) start date < Study Treatment start date (If the medication end date is not missing and is before 28 days prior to screening visit)
On-Treatment	If CM start date < Study Treatment start date and CM stop date ≥ Study Treatment start date or If Study Treatment start date < CM start Date < Last Dose of Study Treatment date + 182 days
Post-Treatment	If CM start date < Last Dose of Study Treatment date + 182 days and CM stop date ≥ Last Dose of Study Treatment date + 182 days Or If CM start Date > Last Dose of Study Treatment date + 182 days

NOTES: Please refer to Section [6.2.6](#): Handling of Missing and Partial Dates for concomitant medication. Use the rules in this table if concomitant medication date is completely missing.

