5.1. Inclusion Criteria

Participants are eligible to be included in the study only if all of the following criteria apply:

Age

1. The study population will consist of adult participants from 18 to 50 years of age inclusive at the time of signing the informed consent.

Type of Participant and Disease Characteristics

2. Participants who are overtly healthy as determined by medical evaluation including medical history, physical examination, clinical laboratory tests, vital sign measurements, and 12-lead ECG results. A participant with a clinical abnormality or laboratory parameters outside the reference range may be included only if the investigator (in consultation with the medical monitor, if necessary) documents that the finding is unlikely to introduce additional risk factors and will not interfere with the study procedures.

Weight

3. Body weight ≥ 50 kg (110 lbs) and body mass index within the range 19 to 30 kg/m² (inclusive).

Sex and Contraceptive/Barrier Requirements

4. Male or female
 - a. Male Participants: as depemokimab is a monoclonal antibody that is not anticipated to interact directly with DNA or other chromosomal material with minimal exposure through semen expected, male participants will not be required to use contraception during the study, nor are they prohibited from donating sperm.
 - b. Female Participants:
 - A female participant is eligible to participate if she is not pregnant or breastfeeding, and one of the following conditions applies:
 - Is not a WOCBP as defined in [Appendix 4](#)
 - OR
 - Is a WOCBP and using a contraceptive method that is highly effective, with a failure rate of $<1\%$, as described in [Appendix 4](#), from at least 14 days prior to administration of the study intervention until at least 30 weeks after administration
 - A WOCBP must have a negative highly sensitive serum pregnancy test at screening and a negative highly sensitive urine pregnancy test within 24 hours before study intervention. If a urine test cannot be confirmed as negative (e.g., an ambiguous result), a serum pregnancy test is required. In such cases, the participant must be

excluded from participation if the serum pregnancy result is positive. Additional requirements for pregnancy testing are located in Section 8.3.5.

- Contraceptive use by WOCBP should be consistent with local regulations regarding the methods of contraception for those participating in clinical studies.

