6.1.4. Prior and Concomitant Medications

Prior and concomitant medication tables will report by Anatomical Therapeutic Chemical (ATC) level 1 and ingredient. Multi-ingredient medications will be presented according to their combination ATC classification rather than the classification of the ingredients.

Summaries will be provided for the concomitant medications taken during treatment.

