	Missing start day and month	
If study intervention start date is missing (i.e. participant did not start study intervention), then set start date = January 1.
 
Else if study intervention start date is not missing:
 
 If year of start date = year of study intervention start date, then 
 If stop date contains a full date and stop date is earlier than study intervention start date, then set start date = January 1. Else set start date = study intervention start date. 
Else set start date = January 1.

	Missing end day	A '28/29/30/31' will be used for the day (dependent on the month and year).
	Missing end day and month	A '31' will be used for the day and 'Dec' will be used for the month.
Age	Completely missing start/end date	No imputation
	
 Age will be calculated based on the Pre-Screening Visit date (or Screening, if pre-screening not performed). 	

Element	Reporting Detail
	
 Only year of birth is collected on eCRF. Day and Month of birth are imputed as 30 June. Age is derived using the date of the screening visit. All participants with imputed age of 17 or 18 years will be source data verified, and presence/ absence of protocol deviation on the inclusion criteria #1 will be taken into consideration in the derivation for the analysis variable age. 
Birth date will be presented in listings as 'YYYY'.

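### SAP 6.2.2.2, read literally, gives no study phase to a medication started before dosing that has no stop date, so it can fall out of the on-treatment medication summary

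*SAP*

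**What the plan says.** SAP 6.2.2.2 assigns each concomitant medication to phases by comparing its dates with the dosing date and with last dose + 182 days.

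- **Pre-Treatment:** started before dosing, with the added condition "If the medication end date is not missing and is before 28 days prior to screening visit".
- **On-Treatment, branch 1:** "If CM start date < Study Treatment start date and CM stop date ≥ Study Treatment start date".
- **On-Treatment, branch 2:** "If Study Treatment start date < CM start Date < Last Dose of Study Treatment date + 182 days".
- **Post-Treatment, branch 1:** started before the 182-day limit and "CM stop date ≥ Last Dose of Study Treatment date + 182 days".
- **Post-Treatment, branch 2:** started after the 182-day limit.

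The note under the table adds: "Use the rules in this table if concomitant medication date is completely missing". In SAP 6.2.6, partial end dates for medications are completed, but the entry for "Completely missing start/end date" rules imputation out. SAP 6.1.4 then states: "Summaries will be provided for the concomitant medications taken during treatment".

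Protocol 6.8 requires every medication in use at enrollment or taken during the study to be recorded, with start and end dates. Protocol 5.1 requires women of childbearing potential to use highly effective contraception "from at least 14 days prior to administration of the study intervention until at least 30 weeks after administration".

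**The concern.** A medication begun before dosing and still in use at the end of the study has no stop date to record. If the phase rule cannot place it, the summary of medications taken during treatment omits a drug that was taken throughout the PK sampling period. The same summary would keep a drug begun before dosing and stopped part-way through.

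The most obvious candidates are hormonal contraceptives. Protocol 5.2.2 and 6.8 bar most other drugs, although case-by-case exceptions are possible. The contraception period in Protocol 5.1 starts before dosing and runs to at least 30 × 7 = 210 days after it, which is about the last follow-up visit at Day 211. A compliant user of a drug-based method would therefore normally have an early start date and an open end date. At stake is whether one descriptive table is complete.

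**Working it through.** No figure in the plan needs reproducing. The check applies each branch of the table to test records.

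**Step 1: a medication started before dosing, stop date missing.**

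1. Pre-Treatment: not met, because the row requires an end date that is present.
2. On-Treatment branch 1: cannot be met, because there is no stop date to compare with dosing.
3. On-Treatment branch 2: not met, because the start is before dosing.
4. Post-Treatment branch 1: cannot be met, because there is no stop date to compare with the 182-day limit.
5. Post-Treatment branch 2: not met, because the start is too early.

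No row applies. SAP 6.2.6 supplies no date, and the table note returns the record to the rules that have just failed.

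**Step 2: neighbouring records.** Days count from dosing (dosing = 0, limit = 182). Screening is assumed at day −20, so the Pre-Treatment cut-off is −20 − 28 = −48.

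| Start | Stop | Rule as written | Ongoing treated as a late stop |
|---|---|---|---|
| −400 | ongoing | none | On and Post |
| −14 | ongoing | none | On and Post |
| −400 | 50 | On | On |
| −400 | 210 | On and Post | On and Post |
| 10 | ongoing | On | On and Post |
| 0 | ongoing | none | Post only |
| 0 | 5 | none | none |
| −60 | −5 | none | none |
| −100 | −60 | Pre | Pre |
| 182 | 190 | none | none |

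The first two rows are the main defect, and an ongoing clause repairs them. It does not repair three other gaps: a start on the dosing day (strict inequalities on both sides), a stop between the 28-day cut-off and dosing, and a start exactly at the 182-day limit.

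**Step 3: size.** The documents give neither the share of women of childbearing potential nor the contraceptive mix. Assume shares of 30–60% and 30–70% respectively, with 140 enrolled (Protocol 9.5):

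- low: 140 × 0.30 × 0.30 = 12.6, about 13
- middle: 140 × 0.50 × 0.50 = 35
- high: 140 × 0.60 × 0.70 = 58.8, about 59

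These are ceilings for contraceptives under each pair of shares. They also require every such user to have started before dosing, to have a blank stop date, and to be covered by no rule elsewhere.

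**Step 4: reach.** The primary model in SAP 4.2.2 uses treatment, injection site and log baseline weight. The estimand in SAP 1.1 keeps PK data after prohibited medication. The exclusion review in SAP 4.8 looks at protocol deviations and SAEs. None of these uses the medication phase.

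**The case against.** The strongest reply is that the intent is clear and the details sit elsewhere. The Pre-Treatment row excludes missing end dates, which suggests that such a drug was not meant to count as prior. A medication taken continuously through dosing is, in plain words, taken during treatment. SAP 1 and 6.1 leave further data-handling conventions and display details to the OPS, which is not available here, and neither document shows how the eCRF codes ongoing use. This stands to the extent that omission is a risk under literal programming and not a stated outcome. It does not remove the defect: the SAP gives a rule, and that rule fails for these records. SAP 6.2.2.3 does state a default for adverse events when the treatment stop date is missing; no such default is given here for medications.

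A reader might also infer more than the documents support:

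- **That the contraceptives the protocol requires all vanish from the table.** The protocol requires a highly effective method, in women of childbearing potential only. Appendix 4 allows an intrauterine device, tubal occlusion or ligation, an azoospermic partner and abstinence. Only drug-based methods are at issue, together with any other permitted medication ongoing from before dosing.
- **That mainly short courses would remain.** On-Treatment branch 2 needs no stop date, so a drug begun after dosing and still ongoing is kept. So is a drug begun before dosing whose full or imputed end date falls on or after dosing.
- **That this is certainly the only medication table.** That is a fair reading of SAP 6.1.4 and of the version-history rationale, but the section still opens by referring to prior and concomitant medication tables in the plural.

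**Conclusion.** The defect holds on the text: a medication started before dosing with no stop date meets no phase definition, and neither SAP 6.2.6 nor the table note rescues it. Because the plan states a rule that misclassifies these records, this is an error in the rule and not just missing detail.

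The consequence is conditional. Such medications would be left out of the on-treatment summary unless the OPS or the eCRF coding supplies a rule. The 13 to 59 participants rest wholly on assumed shares and should not be quoted as an estimate from the plan.

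A reader might go on to infer that the comparison of autoinjector and syringe is affected. It is not, because no PK analysis or PK exclusion rule uses this variable. Severity is minor: one descriptive table.

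**What to change.** In SAP 6.2.2.2:

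1. Extend On-Treatment branch 1 so that its stop-date condition is met either by a stop on or after dosing or by the record being marked ongoing.
2. Add the same ongoing alternative to Post-Treatment branch 1.
3. Use ≤ at the dosing date in On-Treatment branch 2, so that a start on the dosing day receives a phase. The same edit can assign a start exactly at last dose + 182 days.
4. State separately that a stop date that is unknown but not marked ongoing counts as On-Treatment by convention, and flag those records. Ongoing and unknown should not be merged, since a drug with an unrecorded end date may have stopped before dosing.
5. Decide explicitly whether the Pre-Treatment cut-off of 28 days before screening stays. If it is changed, say so in the version history, and make sure that medications stopped between the cut-off and dosing receive a phase.

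The OPS should carry the same wording. The cost is a few lines of SAP text and a small change to the derivation code. No new data are needed if the eCRF already marks ongoing use; if it does not, the convention in item 4 covers every blank stop date.

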6.2.6. Handling of Partial Dates

Element	Reporting Detail								
General	
 Partial dates will be displayed as captured in participant listing displays. However, where necessary, display macros may impute dates as temporary variables for sorting data in listings only. In addition, partial dates may be imputed for 'slotting' data to study phases or for specific analysis purposes as outlined below. Imputed partial dates will not be used to derive study day, time to onset or duration (e.g., time to onset or duration of adverse events), or elapsed time variables (e.g., time since diagnosis). In addition, imputed dates are not used for deriving the last contact date in overall survival analysis dataset. 								

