Missing start day	
If study intervention start date is missing (i.e. participant did not start study intervention), then set start date = 1st of month.
 
Else if study intervention start date is not missing:
 
 If month and year of start date = month and year of study intervention start date, then 
 If stop date contains a full date and stop date is earlier than study intervention start date, then set start date= 1st of month. Else set start date = study intervention start date. 
Else set start date = 1st of month.
								
Missing start day and month	
If study intervention start date is missing (i.e. participant did not start study intervention), then set start date = January 1.
 
Else if study intervention start date is not missing:
 
 If year of start date = year of study intervention start date, then 
 If stop date contains a full date and stop date is earlier than study intervention start date, then set start date = January 1. Else set start date = study intervention start date. 
Else set start date = January 1.
								
Missing end day	A '28/29/30/31' will be used for the day (dependent on the month and year).								
Missing end day and month	No Imputation								

Element	Reporting Detail	
	Completely missing start/end date	No imputation
Concomitant Medications	
 Partial dates for any concomitant medications recorded in the CRF will be imputed using the following convention: 	
	Missing start day	
If study intervention start date is missing (i.e. participant did not start study intervention), then set start date = 1st of month.
 
Else if study intervention start date is not missing:
 
 If month and year of start date = month and year of study intervention start date, then 
 If stop date contains a full date and stop date is earlier than study intervention start date, then set start date= 1st of month. Else set start date = study intervention start date. 
Else set start date = 1st of month.

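### The SAP's concomitant-medication phase rule cannot classify a medication started, or imputed to start, on the dosing day as On-Treatment, so the record drops out of the during-treatment summary

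*SAP*

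**What the plan says.** SAP Section 6.2.2.2 sorts concomitant medications (CM) into three phases.

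- **Pre-Treatment:** "Concomitant medication (CM) start date < Study Treatment start date", with an added condition in parentheses that the end date is known and falls before 28 days prior to screening.
- **On-Treatment, clause 1:** "If CM start date < Study Treatment start date and CM stop date ≥ Study Treatment start date".
- **On-Treatment, clause 2:** "If Study Treatment start date < CM start Date < Last Dose of Study Treatment date + 182 days".
- **Post-Treatment, clause 1:** a start strictly before last dose + 182 days, with a stop on or after that day.
- **Post-Treatment, clause 2:** a start strictly after last dose + 182 days.

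Section 6.2.6 covers partial dates and states: "In addition, partial dates may be imputed for 'slotting' data to study phases or for specific analysis purposes as outlined below". For concomitant medications with a missing start day, the rule applies when month and year match dosing. With day and month both missing, it applies under "If year of start date = year of study intervention start date, then". In either case a full stop date earlier than dosing moves the start to the first of the month or to 1 January. Otherwise the instruction is "Else set start date = study intervention start date".

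Section 6.1.4 gives the planned output: "Summaries will be provided for the concomitant medications taken during treatment".

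The parallel rules for safety assessments (Section 6.2.2.1) and adverse events (Section 6.2.2.3) define On-Treatment with less-than-or-equal at both the dosing date and last dose + 182 days.

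**The concern.** The dosing date is one of the dates on which the phase rule has to work, and the medication rule leaves it out. An adverse event that starts on Day 1 is on-treatment under Section 6.2.2.3. A medication started that day, for that event or for any other reason, is not on-treatment under Section 6.2.2.2.

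The imputation rule makes this worse. Its evident purpose is to be inclusive: when the start is uncertain and could fall on or after dosing, it is set to the dosing date. The phase rule then excludes exactly that date, so records that the SAP means to keep are dropped.

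At stake is the completeness of the summary of medications taken during treatment. A program that follows the SAP to the letter would under-report it without any visible error.

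**Working it through.** **Inputs.** All phase and imputation rules come from SAP Sections 6.2.2.2 and 6.2.6. The study gives a single dose (SAP Section 1.2), so the last dose date equals the treatment start date. Write D for the dosing date, s for the medication start and e for its stop. Under SAP Section 6.2.3, D is Study Day 1 and D + 182 is Study Day 183. An ongoing medication is assumed to satisfy any condition that the stop is on or after a date.

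**Step 1: each clause at s = D.**

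| Clause | Condition | At s = D |
|---|---|---|
| Pre-Treatment | s < D, plus end-date condition | false |
| On-Treatment 1 | s < D and e ≥ D | false |
| On-Treatment 2 | D < s < D + 182 | false |
| Post-Treatment 1 | s < D + 182 and e ≥ D + 182 | true only if e ≥ D + 182 |
| Post-Treatment 2 | s > D + 182 | false |

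**Step 2: all stop dates for s = D.** Stop days D + 0 to D + 210 (Day 211, the last follow-up) give 211 cases. Adding ongoing makes 212.

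- e from D to D + 181: 182 cases, no phase.
- e from D + 182 to D + 210 (29 cases) plus ongoing (1): 30 cases, Post-Treatment only.
- On-Treatment: 212 − 182 − 30 = 0 cases.

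These counts test the logic. They are not an expected share of real records.

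**Step 3: neighbouring start dates.**

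| Start | Stop D + 5 | Stop D + 182 |
|---|---|---|
| D − 1 | On | On and Post |
| D | none | Post only |
| D + 1 | On | On and Post |

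Only the boundary date fails.

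**Step 4: partial dates.** Dosing is assumed on 14 March 2023, for illustration only.

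| Recorded start | Stop | Imputed start | Phase as written |
|---|---|---|---|
| March 2023 | 20 March 2023 | 14 March | none |
| 2023 | 1 June 2023 | 14 March | none |
| March 2023 | ongoing | 14 March | Post only |
| March 2023 | 10 March 2023 | 1 March | not imputed to dosing day |
| April 2023 | ongoing | 1 April | On and Post |

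**Step 5: two further gaps in the same table.**

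- s = D + 182: On-Treatment 2 and Post-Treatment 1 both need s < D + 182, and Post-Treatment 2 needs s > D + 182. No clause is met, whatever the stop date.
- s < D and e < D, but e not before 28 days prior to screening: Pre-Treatment fails on its end-date condition and On-Treatment 1 fails on e ≥ D. With screening assumed at D − 30, the cut-off is D − 58. A course from D − 40 to D − 5 then has no phase, while one from D − 100 to D − 59 is Pre-Treatment. This gap does not touch the during-treatment table, because such a medication was not taken during treatment.

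**Step 6: after the change.** With D ≤ s in On-Treatment 2, all 212 cases in Step 2 become On-Treatment: 182 On only, and 30 On and Post. With s ≤ D + 182 at the upper end, a start on D + 182 is also On-Treatment.

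**The case against.** The best defence is that this is a drafting slip with plain intent. Sections 6.2.2.1 and 6.2.2.3 show what was meant, a programmer may well code it that way, and the display details are deferred to the Output and Programming Specification (OPS), which is not available here. The volume is probably small: participants are healthy and must largely abstain from other drugs, although paracetamol is allowed (protocol Section 6.8). No data are lost, since the protocol requires every medication to be recorded in the eCRF. All of this limits the importance of the point, and it stands. It does not make the stated rule right. Nor is a lost symbol in the PDF text a likely explanation, because the same table keeps its greater-than-or-equal signs.

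Several stronger readings are tempting, and the documents do not support them.

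- *That this is the only medication table.* Section 6.1.4 does not say so. It also mentions prior and concomitant medication tables; the word only appears in the version history.
- *That the loss falls on treatment for injection-related symptoms.* Nothing in the documents says that such use concentrates on Day 1. Protocol Section 2.3.1 reports injection site reactions in one depemokimab participant (3%) in the first-in-human study. SAP Section 4.5.2 summarises local injection site reactions from a targeted eCRF, independently of medication phase.
- *That every partial start date falls in the gap.* Records with a full stop date before dosing are moved elsewhere, and those whose known month or year differs from dosing are not set to the dosing date.
- *That no dosing-day start has any phase, or that long courses escape the problem.* Courses reaching Day 183 do get Post-Treatment, but they are still absent from On-Treatment.

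**Conclusion.** The rule is wrong as written. No medication with an actual or imputed start on the dosing date can be On-Treatment, and all such records are missing from the during-treatment summary. Those stopped before last dose + 182 days have no phase; those stopped on or after it, or ongoing, are at most Post-Treatment. A start exactly on last dose + 182 days also has no phase.

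The size is modest. The effect is confined to descriptive concomitant-medication reporting. The primary PK model does not use these phases, prohibited medication is handled by a treatment-policy strategy, and adverse-event phases have their own correct rule. How many records are affected cannot be derived from the documents.

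The conclusion rests on reading the inequalities literally, on imputed dates being used for phase assignment as Section 6.2.6 permits, and on the OPS not overriding the rule.

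**What to change.** In SAP Section 6.2.2.2:

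1. Change the second On-Treatment clause to: dosing date ≤ medication start ≤ last dose + 182 days. This matches Sections 6.2.2.1 and 6.2.2.3 and closes both boundary gaps.
2. Keep the second Post-Treatment clause as a start strictly greater than last dose + 182 days.
3. Define Pre-Treatment as a stop date before the treatment start date. This closes the third gap.

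Section 6.2.6 needs no change; once the first edit is made, its imputed dates fall in On-Treatment. The cost is two inequality signs, one rewritten Pre-Treatment line and the matching program edits, plus a check that the OPS agrees. No new data and no design change are needed.
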